SOP	Standard Operating Procedure
SPC	Summary of Product Characteristics
SSA	Site Specific Assessment
SUSAR	Suspected Unexpected Serious Adverse Reaction
TMG	Trial Management Group
TSC	Trial Steering Committee
UMSARS	Unified Multiple System Atrophy Rating Scale

1 Trial personnel

See protocol cover page for Chief Investigator and Sponsor contact details.

Statistician

[name]

Joint Research Office (Research Support Centre), 1st Floor
[name]
Email: [contact]

[contact]

Trial Management

Leonard Wolfson Experimental Neuroscience Centre
National Hospital for Neurology & Neurosurgery
[name]
London
[name]

Central labs

National Hospital for Neurology & Neurosurgery
[name]
London
[name]

Head of Department

[name]
National Hospital for Neurology & Neurosurgery
[name]
London
[name]

2 Summary

Objectives:

Primary Objective

To collect pilot data from which to estimate the effectiveness of Exenatide in modifying disease progression of patients with Multiple System Atrophy. The primary endpoint will be the difference in total Unified Multiple System Atrophy Rating Scale (UMSARS) score (Parts I and II) at 48 weeks comparing exenatide to best medically treated patients.

Secondary Outcomes

- The proportion of patients with loss of independent ambulation by the end of the study, defined by a score of 4 or more in UMSARS-I item 7 (walking),
- The difference at week 48 in the MSA-QoL scale,
- The difference at week 48 in UMSARS parts III and IV,
- The difference in anti-parkinsonian or anti-orthostatic hypotension drugs,
- The number of falls,
- The proportion of patients reaching a score of 3 or more on UMSARS-I items 1 (speech), 2 (swallowing), and 8 (falling),
- The difference at week 48 in clinical global impression (CGI); difference at week 48 in MoCA scores.

Exploratory Outcomes

- The difference in total Unified Multiple System Atrophy Rating Scale (UMSARS) score (Parts I and II) at 96 weeks comparing exenatide to best medically treated patients,
- The difference at 96 weeks in the MSA-QoL scale comparing exenatide to best medically treated patients,
- The difference at 96 weeks in UMSARS parts III and IV comparing exenatide to best medically treated patients,
- The difference in anti-parkinsonian or anti-orthostatic hypotension drugs at 96 weeks comparing exenatide to best medically treated patients,
- The difference in the number of falls at 96 weeks comparing exenatide to best medically treated patients,
- The difference in the proportion of patients reaching a score of 3 or more on UMSARS-I items 1 (speech), 2 (swallowing), and 8 (falling) at 96 weeks comparing exenatide to best medically treated patients,

Short title: Exenatide once-weekly as a treatment for Multiple System Atrophy Sponsor code: 125591

- The difference at 96 weeks in clinical global impression (CGI) and MoCA scores comparing exenatide to best medically treated patients.

Type of trial: Phase IIa, open label, randomised, parallel group, single site trial in Multiple System Atrophy.

Trial design and methods: Fifty patients with early stage MSA will be recruited and randomised to receive Exenatide injections, or to act as controls in this open label trial. Exenatide will be given as a once weekly subcutaneous injection in addition to participant's regular medication. All patients will continue to receive standard of care treatment for MSA. Detailed assessments will be made of all patients at baseline and periodically for a total of 96 weeks. The primary endpoint will be the difference in total Unified Multiple System Atrophy Rating Scale (UMSARS) score (Parts I and II) at 48 weeks comparing Exenatide to best medically treated patients. Secondary measures will include adverse event reports, self-completed questionnaires, and blood test results. Aside from these assessments, all patients will continue any regular MSA medications throughout the trial with adjustments made only according to clinical need.

Estimated total trial duration: 96 weeks per patient

duration: 48 months total trial duration.

Planned trial sites: Single-site- National Hospital for Neurology & Neurosurgery.

Total number of participants planned: 50 participants.

Main inclusion/exclusion criteria: **Inclusion Criteria**

Participants aged 30-80 years old with a diagnosis of Possible or Probable MSA of the parkinsonian subtype (MSA-P) or cerebellar subtype (MSA-C) according to The Gilman Criteria (Gilman et al. 2008)

Participants who are less than five years from the time of documented MSA diagnosis or from the time of documented parkinsonian / ataxic neurological condition that later turns out to be MSA.

Participants who are able to walk at least 10 metres with or without assistance.

Participants with an anticipated survival of at least three years in the opinion of the investigator.

Participants that are willing to adhere to the study drug regimen.

Participants that are willing and able to perform all protocol-specified assessments and comply with the study visit schedule.

Females of childbearing potential and male participants with partners of childbearing potential agree to use an effective method of contraception from the time consent is signed until 10 weeks after treatment discontinuation.

Females of childbearing potential have a negative pregnancy test within 7 days prior to being randomised.

Willing and able to provide written informed consent. Subjects who are not able to write may give verbal consent in the presence of at least one witness, and the witness should sign the informed consent form.

Exclusion Criteria

Females who are pregnant, planning pregnancy or breastfeeding.

Women of child-bearing potential who do not practice an acceptable method of birth control.

Subjects who meet any of the following criteria which tend to suggest advance disease:

1. Speech impairment as assessed by a score of ≥ 3 on UMSARS question 1
2. Swallowing impairment as assessed by a score of ≥ 3 on UMSARS question 2
3. Impairment in ambulation as assessed by a score of > 3 on UMSARS question 7
4. Falling more frequently than once per week as assessed by a score of ≥ 3 on UMSARS question 8.

Participants with a clinically significant or unstable medical or surgical condition, which in the opinion of the investigator might preclude safe completion of the study.

Participants with active malignant neoplasms or history of malignant neoplasm in the last 5 years.

Participants with movement disorders other than MSA.

Concurrent dementia defined by a score lower than 21 on the MoCA.

Short title: Exenatide once-weekly as a treatment for Multiple System Atrophy Sponsor code: 125591

Concurrent severe depression defined by a score of ≥ 30 on the Beck Depression Inventory-II.

History of deep brain stimulation surgery.

Participants who have taken any investigational products within 90 days prior to baseline.

Participants with a BMI < 18.5 .

Participants with diabetes, end stage renal disease or severely impaired renal function with creatinine clearance $< 30 \text{ ml/min}$.

History of clinically significant cardiac disease, pancreatitis and/or alcoholism.

Participants with severe gastrointestinal disease including gastroparesis.

Ongoing treatment with sulphonylurea.

Known allergies to the IMP and excipients of IMP.

Statistical methodology and analysis:

The primary endpoint will be the difference in total Unified Multiple System Atrophy Rating Scale (UMSARS) score (Parts I and II) at 48 weeks comparing Exenatide to best medically treated patients. The main statistical analysis of the primary endpoint will be based on the intent-to-treat population (ITT). The analysis will use ANCOVA to allow adjustment for baseline severity and MSA subtype.

3 Background and Rationale

Multiple System Atrophy (MSA) is a rare, progressive neurodegenerative disorder clinically characterized by autonomic dysfunction, parkinsonism and cerebellar impairment. Like Parkinson's disease (PD) and Dementia with Lewy bodies (DLB), MSA is a synucleinopathy and the pathological correlate is the formation of glial cytoplasmic inclusions, composed of accumulated alpha-synuclein. Despite sharing many clinical similarities with PD, unlike PD, there are no effective symptomatic therapies available and no approaches for slowing disease progression, meaning the average survival time from diagnosis is around 6-9 years (Fanciulli and Wenning 2015). There is thus a great unmet need for neuroprotective or disease modifying therapies.

Accumulating data suggest that Exenatide, a glucagon-like peptide-1 (GLP-1) agonist used in the treatment of Type 2 diabetes (T2DM) may offer a novel approach to treating MSA (Bassil et al. 2017). Numerous epidemiological studies have indicated T2DM is a risk factor for developing Alzheimer's disease, PD and other neurodegenerative diseases. Patients with T2DM have 30-40% increased risk of developing PD, while patients with PD and T2DM have a more aggressive disease course, and require increasing amounts of medication (De Pablo-Fernandez et al. 2017; D'Amelio et al. 2009).

Studies have suggested that these age-related diseases share dysfunctional insulin signaling linking diabetes and neurodegeneration. Via insulin receptors found throughout the brain, insulin is responsible for modulating many cellular processes including inflammation, protein aggregation, oxidative stress, autophagy and apoptosis, via the actions of two main downstream pathways Akt and MAPK (Talbot et al. 2012; Athauda and Foltynie 2016). Importantly, these dysregulation of processes are thought to be involved in the pathogenesis of MSA.

Peripheral insulin and insulin-like growth factor levels are increased in the serum of MSA patients and this has been shown to correlate with disease progression, suggesting a link between insulin signalling and MSA (Bassil et al. 2017; Bassil et al. 2017). More recently, a study by Bassil et al. has shown evidence of insulin resistance in the brains of patients with MSA. A measure of insulin resistance is the amount of the downstream messenger insulin receptor substrate-1 (IRS-1) phosphorylated at serine residues 312 (IRS-1pS312) or 616 (IRS-1pS616) and the authors demonstrated increased expression of these markers of insulin resistance that occurred in the context of neuronal cell loss compared to controls. Therefore, if insulin resistance occurs in the brain in MSA, modulating insulin/IGF-1 signalling might provide an effective approach to disease modification.

Exenatide has been a treatment licensed for use in Type 2 diabetes since 2005 and activates the GLP-1 receptor. The GLP-1 receptor is expressed throughout the brain and activates similar pathways to those of insulin (Cork et al. 2015). Previous studies have shown that activation of this receptor by Exenatide has protective effects in models of PD, Alzheimer's disease, stroke, Huntington's disease and multiple sclerosis through positive effects on cell survival, apoptosis, and protein aggregation (Athauda and Foltynie 2016; Greig et al. 2014).

Indeed, a recent study using Exenatide in a transgenic mouse model of MSA showed that Exenatide treatment had positive effects on insulin resistance and monomeric alpha-synuclein

Short title: Exenatide once-weekly as a treatment for Multiple System Atrophy Sponsor code: 125591

levels in the striatum, as well as improving survival of nigral dopamine neurons (Bassil et al. 2017).

Based on these encouraging data, 2 clinical trials of Exenatide in patients with moderate stage PD have been conducted.

A small, “proof-of-concept” open-label phase 2 clinical trial evaluating the safety and efficacy of Exenatide in PD which showed a significant improvement in motor scores and cognitive efficiency at 12 months in patients with PD treated with Exenatide compared to a control group, which persisted following drug withdrawal (Aviles-Olmos et al. 2013, 2014). Despite the open-label design, this study demonstrated that a drug in clinical use for another medical condition could be successfully tested for its disease-modifying effects in patients with PD using standard clinical measures, without the need to include a placebo-controlled arm, in a relatively inexpensive way. The aim of the open label trial was to provide proof of concept of possible efficacy to reassure investment into more formal double blind placebo controlled efficacy trials.

Following on from this, a fully randomised, placebo-controlled trial of Exenatide in patients with moderate stage PD was conducted, which replicated the results of the previous open label trial and showed Exenatide reduced motor severity of PD compared to placebo. Exenatide was well-tolerated in this patient group and it was shown for the first time that peripherally administered Exenatide crossed the blood brain barrier and is detectable in the cerebrospinal fluid at a ratio of around 3% of that detected in serum (Athauda et al. 2017). Post hoc analysis also indicated possible beneficial effects on depression which can be a major contributor to morbidity in both PD and MSA (Athauda et al. 2018). Using patient serum, we isolated and analysed neuronal derived exosomes to assess target engagement and demonstrated that Exenatide appears to normalise brain insulin signalling with subsequent activation of downstream effectors Akt and mTOR (Athauda et al. 2019).

These encouraging results have set the ground for translation into early clinical trials of Exenatide in further neurodegenerative diseases.

Clinical trials in MSA can be conducted with smaller group sizes, due to the marked faster disease progression of MSA compared with that of PD (Fernagut et al. 2014). In addition, previous studies have demonstrated a consistent rate of progression in the Unified Multiple System Atrophy Rating Scale (UMSARS) Part II (Motor examination) (Wenning et al. 2004, 2013; Low et al. 2015; Dodel et al. 2010; Poewe, Hauser, and Lang 2015; Low et al. 2014)

There are no effective treatments that can slow down or modify the course of disease progression. MSA has a prevalence of 4.4 in 100,000 individuals and affects males and females equally. Currently, treatment strategies focus on symptomatic control of parkinsonism, autonomic dysfunction and mood problems. However, despite this, the prognosis remains poor with average survival of eight years. There is thus an urgent unmet need for novel treatments that may slow or halt disease progression in MSA. Patients with MSA require care from a range of services, and as the disease progresses these care needs increase, thus a disease modifying treatment would have a massive impact on caregivers and social services.

Based on prevalence figures of MSA, the estimated annual healthcare costs associated with MSA are estimated to be €1.1–3.0 billion across 27 countries in the European Union. Unpaid care accounts for 68–76%. If an intervention were to reduce the rate of disease progression even by

Short title: Exenatide once-weekly as a treatment for Multiple System Atrophy Sponsor code: 125591

30%, the costs to services would be 9-10% lower and 7-12% lower in unpaid care costs. Preliminary data obtained by this study would provide an urgent impetus for further funding for a larger scale study to assess the effects of Exenatide and other GLP-1 agonists in a wider population of MSA patients.

3.1 Assessment and management of risk

The table below summarises the risks, frequencies and mitigations of the IMP(s)

Name of IMP(s) / NIMP	Potential risk	Risk Frequency	Risk Management
Exenatide	Weight loss	Common	Underweight people will not be recruited. Patients losing weight too rapidly (>10% body weight per month) will temporarily stop the IMP.
Exenatide	Nausea/ Vomiting	Very common	In most cases, nausea is mild and self limiting. In more severe cases, patients will be prescribed a temporary course of Domperidone.
Exenatide	Diarrhoea	Very common	In most cases, diarrhoea is mild and self limiting. Symptomatic and supportive treatment will be given as necessary.
Exenatide	Decreased Appetite	Common	In most cases, loss of appetite is transient and self limiting. Weight will be measured and exenatide will be transiently stopped if weight loss exceeds 10% of body weight per month.
Exenatide	Headache	Common	In most cases, headache is transient and self limiting. Participants will be assessed and given standard of care treatment for persistent headaches.
Exenatide	Dizziness	Common	In most cases, dizziness, is transient and self limiting. Participants will be assessed and given standard of care treatment for persistent dizziness.

Short title: Exenatide once-weekly as a treatment for Multiple System Atrophy Sponsor code: 125591

Exenatide	Dyspepsia/ Abdominal pain	Common	In most cases, abdominal pain is transient and self limiting. Any suspicion of pancreatitis will lead to temporary discontinuation of exenatide until pancreatitis has been excluded. Participants will be assessed and given standard of care treatment for persistent abdominal pain.
Exenatide	Abdominal Distension/ Flatulence	Common	In most cases, abdominal distension/flatulence is transient and self limiting. Participants will be assessed and given standard of care treatment for persistent abdominal distension/flatulence.
Exenatide	Constipation	Common	In most cases, constipation is transient and self limiting. Participants will be assessed and given standard of care treatment for persistent constipation.
Exenatide	Anaphylactic reaction	Rare	Patients will self administer their first Exenatide injection in the trial centre under supervision by the trial team.

The table below summarise the risks and mitigations of all test above standard care that are being performed in a table:

Intervention	Potential risk	Risk Management
Blood tests	Bruising at phlebotomy site	Compression will be applied to minimise bruising.
Lumbar puncture	Post lumbar puncture headache.	Atraumatic needles will be used which have been shown to minimise the risk of post lumbar puncture headache.

In accordance with the MRC/DH/MHRA Joint Project Risk-adapted Approaches to the Management of Clinical Trials of Investigational Medicinal Products, this trial is categorised as:

Type B = Somewhat higher than the risk of standard medical care:

This trial is involving a medicinal product licensed in the EU Member State and is being used for a new indication.

4 Objectives

Primary:

The primary endpoint will be the difference in total Unified Multiple System Atrophy Rating Scale (UMSARS) score (Parts I and II) at 48 weeks comparing exenatide to best medically treated patients.

Secondary:

- The proportion of patients with loss of independent ambulation by the end of the study, defined by a score of 4 in UMSARS-I item 7 (walking),
- The difference at week 48 in the MSA-QoL scale,
- The difference at week 48 in UMSARS parts III and IV,
- The difference in anti-parkinsonian or anti-orthostatic hypotension drugs,
- The number of falls,
- The proportion of patients reaching a score of 3 or more on UMSARS-I items 1 (speech), 2 (swallowing), and 8 (falling),
- The difference at week 48 in clinical global impression (CGI)
- The difference at week 48 in MoCA scores.
- Safety of exenatide in MSA based on Adverse event reporting

Exploratory

- The difference in total Unified Multiple System Atrophy Rating Scale (UMSARS) score (Parts I and II) at 96 weeks comparing exenatide to best medically treated patients,
- The difference at 96 weeks in the MSA-QoL scale comparing exenatide to best medically treated patients,
- The difference at 96 weeks in UMSARS parts III and IV comparing exenatide to best medically treated patients,
- The difference in anti-parkinsonian or anti-orthostatic hypotension drugs at 96 weeks comparing exenatide to best medically treated patients,
- The difference in the number of falls at 96 weeks comparing exenatide to best medically treated patients,
- The difference in the proportion of patients reaching a score of 3 or more on UMSARS-I items 1 (speech), 2 (swallowing), and 8 (falling) at 96 weeks comparing exenatide to best medically treated patients,
- The difference at 96 weeks in clinical global impression (CGI) and MoCA scores comparing exenatide to best medically treated patients.

Data regarding walking will be collected over a week long period at baseline and at week 48 prior to the visit via a CE marked sensor attached to the lower back – Axivity device.

5 Trial design

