Patients developing clinical suspicion of thyroid malignancy will receive treatment according to NHS standard of care and the trial medication will be stopped.

Patients experiencing excessive/undesirable weight loss (>10% of body weight during a 12 week interval) or unacceptable adverse effects will have a clinical assessment and a decision regarding temporary withdrawal of study medication will be made.

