8.4 Subsequent assessments and procedures

Week 4 (+/-1 week) – telephone call

The study nurse will call the participants to ensure the participants are taking their medication according to the protocol requirements and completing their trial diary as required. They will also perform a concomitant medication and AE check.

Week 12 assessments – Visit 3

At 12 weeks after baseline evaluation, each patient will be telephoned 1 week prior to remind them of their visit

Participants will attend the research centre for the following trial procedures:

- Physical Examination (if deemed necessary by trial clinician for clinical purposes)
- Routine blood tests (FBC, U&E, LFT, glucose, amylase, HbA1c, PT and APTT)
- Serum collection
- Vital signs including weight
- UMSARS Part II (videotaped)
- UMSARS Part I, III and IV
- The Unified Dystonia Rating Scale
- MoCA
- Timed Motor tests
- BDI-II
- Concomitant Medications review
- Adverse Events review
- Dispensing of 12 exenatide (Bydureon or Bydureon BCise) pens (if randomised to receive exenatide).

All participants will be invited for face to face visits at all timepoints. If a participant is unable or unwilling to attend any of the follow up assessments (12,24,36,48,96 weeks), they may be offered the option of a home visit by one or more members of the trial clinical team if staffing levels permit. These participants will be asked to consent to home visits. Assessments will be performed as per protocol. Weight will be measured only if the participant is able to stand, and weighing scales are available. Dispensing of IMP will be performed by trial pharmacy and transported to the patient in an appropriate Cool Bag with temperature logger by the clinical trial team.

Week 24 assessments – Visit 4

At 24 weeks after baseline evaluation, each patient will be telephoned 1 week prior to remind them of their visit. They will be asked not to have eaten and to have drunk water only for 6 hours to enable fasting blood samples to be taken.

Participants will attend the research centre for the following trial procedures:

- Physical Examination (if deemed necessary by trial clinician for clinical purposes)
- Neurological Examination (if deemed necessary by trial clinician for clinical purposes)
- Fasting blood tests (FBC, U&E, LFT, glucose, amylase, insulin, c-peptide, HbA1c)
- Serum collection
- Vital signs including weight
- UMSARS Part II (videotaped)

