Short title: Exenatide once-weekly as a treatment for Multiple System Atrophy Sponsor code: 125591

- UMSARS Part I, III and IV
- Timed motor tests
- COMPASS Select
- COMPASS Change
- The Unified Dystonia Rating scale
- BDI-II
- MoCA
- Concomitant Medications review
- Adverse Events review
- Dispensing of 12 exenatide pens (if randomised to receive exenatide).

Week 36 assessments – Visit 5

At 36 weeks after baseline evaluation, each patient will be telephoned 1 week prior to remind them of their visit.

Participants will attend the research centre for the following trial procedures:

- Physical Examination (if deemed necessary by trial clinician for clinical purposes)
- Routine blood tests (FBC, U&E, LFT, glucose, amylase and HbA1c)
- Serum collection
- Vital signs including weight
- UMSARS Part II (videotaped)
- UMSARS Part I, III and IV
- Timed motor tests
- The Unified Dystonia Rating scale
- BDI-II
- MoCA
- Concomitant Medications review
- Adverse Events review
- Dispensing of 12 exenatide (Bydureon or Bydureon BCise) pens (if randomised to receive exenatide).

Week 48 assessments – Visit 6

At 48 weeks after baseline evaluation, each patient will be telephoned 1 week prior to remind them of their visit. They will be asked not to have eaten and to have drunk water only for 6 hours to enable fasting blood samples to be taken.

Participants will attend the research centre for the following trial procedures:

- Physical Examination (if deemed necessary by trial clinician for clinical purposes)
- Neurological Examination (if deemed necessary by trial clinician for clinical purposes)

Short title: Exenatide once-weekly as a treatment for Multiple System Atrophy Sponsor code: 125591

- Fasting blood tests (glucose, insulin and c-peptide)
- Routine blood tests (FBC, U&E, LFT, glucose, amylase, HbA1c, PT and APTT)
- Serum collection
- Lumbar puncture for CSF collection
- Vital signs including weight
- UMSARS Part II (videotaped)
- UMSARS Part I, III and IV
- Timed motor tests
- COMPASS Select
- COMPASS Change
- MSA-QoL scale
- The Unified Dystonia Rating scale
- BDI-II
- MoCA
- Concomitant Medications review
- Adverse Events review
- Axivity lumbar sensor

If a patient cannot attend the clinical research facility and is being assessed via a home visit, no attempt will be made to perform a lumbar puncture and this missed assessment will be recorded as a protocol deviation.

Week 58 (+/-1 week) telephone call

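### Protocol 3.1 stops exenatide for weight loss above 10% per month, while 8.3.1 calls for assessment and a decision above 10% over 12 weeks; nothing reconciles the two rules

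*Protocol*

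**What the plan says.** Two rows of the IMP risk table in Protocol 3.1 (Assessment and management of risk) give a monthly rule in mandatory wording.

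- Weight loss row: "Patients losing weight too rapidly (>10% body weight per month) will temporarily stop the IMP".
- Decreased Appetite row: "Weight will be measured and exenatide will be transiently stopped if weight loss exceeds 10% of body weight per month".

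Protocol 8.3.1 (Dose Modifications) gives a different rule. Its trigger is "Patients experiencing excessive/undesirable weight loss (>10% of body weight during a 12 week interval"), with unacceptable adverse effects as an alternative trigger. Its action is that such patients "will have a clinical assessment and a decision regarding temporary withdrawal of study medication will be made".

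The table in 3.1 is introduced as a summary of risks and mitigations and lists weight loss as a common effect of exenatide.

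**The concern.** The two places share the 10% figure but differ in the window (a month against 12 weeks) and in the action (a stop against an assessment and a decision). The monthly wording appears in two rows, so it is not a single slip of the pen.

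These are the only weight-specific thresholds for interrupting exenatide in the protocol. If a participant loses weight quickly, the investigator cannot tell from the document whether stopping is required or a matter of judgement. A clinician who assesses such a patient and continues dosing complies with 8.3.1 and departs from 3.1. Whether that is a protocol deviation has no clear answer. The stake is consistent safety conduct, not the efficacy result.

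**Working it through.** The plan gives no figure of its own to reproduce here. The check compares the two texts and then puts both thresholds on one time scale.

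**1. Side by side**

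| | 3.1 (two rows) | 8.3.1 |
|---|---|---|
| Threshold | >10% of body weight | >10% of body weight |
| Window | one month | 12 weeks |
| Action | temporary stop, mandatory | clinical assessment, then a decision on temporary withdrawal |

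**2. Search for a reconciling sentence.** Sections 8.8 and 8.10 give general reasons for discontinuation. Appendix 2 (COVID-19 plans) only includes weight among the telephone questions before dispensing. The SAP does not address the rule. None of these says which rule prevails or describes two tiers.

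**3. Which patients meet which rule**

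- *More than 10% lost within a month and not regained*, for example 11%. This meets 3.1 (must stop). It also exceeds 10% within a 12-week interval, so it meets 8.3.1 (assess, may continue). The instructions conflict.
- *More than 10% lost over 12 weeks, but never more than 10% in any month.* Only 8.3.1 applies; 3.1 is silent.

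**4. Where the second group ends, at a steady rate of loss.** Let m be the number of months in 12 weeks: m = 12/(52/12) = 2.769 for calendar months, or m = 3 for four-week months. The 12-week loss that corresponds to 10% per month depends on how the percentage is counted:

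| Convention | Formula | m = 2.769 | m = 3 |
|---|---|---|---|
| Constant percentage of current weight (compounded) | 1 − 0.9^m | 25.3% | 27.1% |
| Constant kg, percentage of starting weight | 0.10 × m | 27.7% | 30.0% |
| Constant kg, last month judged against weight at its start | m × 0.10/(1 + 0.10(m − 1)) | 23.5% | 25.0% |

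The upper end is therefore about 25%, with a range of about 23.5% to 30%.

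**5. The same comparison per month (compounded).** A loss of 10% over 12 weeks is 1 − 0.9^(1/m) = 3.7% per calendar month or 3.5% per four-week month. A loss of 15% over 12 weeks is 1 − 0.85^(1/m) = 5.7% or 5.3%. Such a patient is well past the 8.3.1 trigger and well short of the 3.1 trigger.

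These loss patterns are illustrative. The documents give no frequencies for them.

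**The case against.** The strongest reply is that the rules are complementary. Section 3.1 speaks of loss that is too rapid, which is a rate; 8.3.1 speaks of excessive or undesirable loss over an interval. Since 8.3.1 permits the stop that 3.1 requires, a careful clinician could satisfy both by always stopping at the monthly threshold and assessing at the 12-week one. This is a sensible reading and would make a good rule, but the protocol does not state it. For rapid loss, 8.3.1 still leaves the stop to judgement.

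It can also be said that this is a single-site trial with 8.3.1 as the natural operative text, and that other protections exist: the BMI exclusion, the unacceptable-adverse-effects clause in 8.3.1, the clinician-judgement stops in 8.8 and 8.10, and adverse event review. That stands. It lowers the seriousness without removing the mismatch.

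A reader might infer three stronger points that the documents do not support.

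- *That patients with slower losses are told by 3.1 to carry on.* Silence in 3.1 is not a competing instruction; 8.3.1 applies to every treated patient.
- *That the 3.1 rows are simply wrong and should be overwritten.* There is some support for this. The pancreatitis entry in 3.1 agrees with 8.3.1, as a summary should, and scheduled on-treatment weights fall 12 weeks apart. But overwriting the rows would remove the only mandatory weight-loss stop, and nothing shows that the less protective text is the intended one.
- *That a monthly rule is unworkable, with a countable number of further doses before detection.* Week 4 lists no weight, but the nurse's call covers adverse events: "They will also perform a concomitant medication and AE check". The appetite row promises weighing without fixing its timing, patients continue to see their treating neurologist (8.3), and visits have a window of plus or minus 7 days. No dose count can be fixed from the documents.

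**Conclusion.** The inconsistency is real and certain on the text, and its scope is limited. The instructions contradict each other only for loss of more than 10% within about a month, where 3.1 requires a stop and 8.3.1 allows continuation. For steady losses from 10% to roughly 25% over 12 weeks there is a difference in coverage, not a contradiction.

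The first statement assumes that the lost weight is not regained within the 12-week interval. The second assumes a steady rate of loss and carries the 23.5% to 30% range for the counting convention.

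This is a minor safety-consistency correction, worth making because it concerns a decision threshold for an effect listed as common. It leaves sample size, power, type I error and the primary analysis untouched.

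**What to change.** Put a single reconciled rule in 8.3.1 and make both 3.1 rows match it. The version that loses no protection has two tiers:

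- more than 10% lost in 12 weeks: clinical assessment and a decision on temporary withdrawal;
- more than 10% lost within a month, whenever detected (scheduled weight, adverse event check or patient report): mandatory temporary stop.

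If the sponsor intends only the 12-week rule, correct the Weight loss and Decreased Appetite rows of 3.1 to the trigger and action in 8.3.1 instead. The choice of threshold and action belongs to the investigators and sponsor.

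The cost is one amendment: about a sentence in 8.3.1 and the wording of two table rows. It needs no additional visits and no SAP change.
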